## **Retrospective Study Period**

Version 5 Revised 5/9/2019

Data collection of adult patients admitted with a primary and secondary diagnosis of Parkinson's disease during January – June 2015.

- Data will be extracted from the EPIC (current EMR system at Hackensack University Medical Center).
- Business intelligence will run the data and create reports with the specific data points mentioned above prior to providing it to the study team for further statistical analysis.

Data collected from the automatic dispensing cabinet barcoding database will verify accuracy and timeliness of medication.

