## **Inclusion Criteria**

1. Adult patients diagnosed with primary and secondary diagnosis of Parkinson's disease
2. Patient 22 years old and older
3. Patients admitted to inpatient units and Center for Ambulatory Surgery
4. Alert and able to follow commands
5. Patient who agree to participate in the study

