## **Exclusion Criteria**

1. Patients less than or equal to 21 years of age
2. Patients who refuse or unable to wear the WatchRx smartwatch
3. Disoriented and unable to follow commands
4. Patients who are allergic to silicone, stainless steel and/or latex
5. Patients positive for Clostridium difficile and/or Candida auris

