## **Study Period**

**Retrospective Data Period:** January 2015 – June 2015

**Prospective Data Period:** After the clinicians have completed the Parkinson's Disease Inpatient Clinical Knowledge and Management Program and the WatchRx Smartwatch is integrated within medication administration for PD medications

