### **Study Enrollment Procedure**

Patients with Parkinson's disease (PD) who meet inclusion criteria will be offered the opportunity to participate in the study. After obtaining informed consent, the patient will be enrolled in the study.

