## **Sample Size Calculation**

A total of 433 patients were admitted to Hackensack University Medical Center with a diagnosis of PD in the year 2014. A convenience sample of 300 patients, 150 patients in the prospective phase and 150 patients in the retrospective phase, and approximately 346 clinicians, before and after implementing the Parkinson's Disease Inpatient Clinical Knowledge and Management education program will be enrolled in the study.

The sample of clinicians will include physician's assistant, advanced practice nurses, staff nurses, nurse educators, case managers, dietitians, pharmacists, physical therapist and occupational therapist. (Table 1)

Categories	Overall population	Sample population	Percentage (Sample size)
Staff Nurses Adult (Inpatient Units)	1931	100	5 %
Nursing Assistants	277	N/A	
Patient Care Technicians	165	N/A	
Advanced Practice Nurses (Adult Inpatient Units)	107	87	81%
Case Managers(Adult Inpatient Units)	48	48	100%
Nurse Educator Adult Inpatient	20	19	95%
Physician's Assistant Adult Inpatient	73	40	54%
Dietitians	17	17	100%
Pharmacists	119	12	11%
Physical Therapist	17	17	100%
Occupational Therapists	6	6	100%

Table 1

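### The eligibility criteria carry no phase labels; on the most natural reading only prospective patients are screened for alertness, which can bias the unadjusted confusion and delirium comparisons

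*Combined protocol and SAP*

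**What the plan says.** Retrospective Study Period describes the 2015 cohort as "Data collection of adult patients admitted with a primary and secondary diagnosis of" Parkinson's disease between January and June 2015. It names no alertness, orientation, infection or allergy criterion and does not refer to the eligibility lists.

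Inclusion Criteria and Exclusion Criteria form a single set with no phase named. Some items could be read from a 2015 chart, such as "Alert and able to follow commands". Others could not: "Patient who agree to participate in the study", and the exclusion of "Patients who refuse or unable to wear the WatchRx smartwatch". Under Study Period, prospective collection begins only after staff training and once "the WatchRx Smartwatch is integrated within medication administration for PD medications".

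Study Enrollment Procedure says that patients "who meet inclusion criteria will be offered the opportunity to participate in the study", followed by informed consent.

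The two lists word the cognitive criterion differently. Inclusion asks for alertness and following commands and does not mention orientation. Exclusion removes those who are "Disoriented and unable to follow commands", which read literally requires both conditions.

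Sample Size Calculation plans "A convenience sample of 300 patients, 150 patients in the prospective phase and 150 patients in the retrospective phase" and does not say how the 2015 records are picked. Secondary Endpoints include the numbers of positive confusion and delirium scores. Data Analysis offers only unadjusted two-group tests. Limitations lists single site and convenience sampling.

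**The concern.** Alertness and orientation lie close to what the confusion and delirium scores measure. If one phase is screened on that trait and the other is not, the phases differ on these endpoints before any training or watch has an effect. The direction is predictable: the unscreened 2015 group looks worse, so the intervention looks better. An unadjusted test cannot separate this from a real effect, so a favourable confusion or delirium result under the second or third hypothesis could be selection alone.

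Falls and length of stay could move the same way, but less. The primary endpoint, the change in clinicians' knowledge score, does not depend on patient eligibility.

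**Working it through.** **Plan's own figure.** 150 + 150 = 300. The plan gives no significance level, power, effect size or event rate for patients, so there is no calculation to reproduce.

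**Reading the sections together.** Applied whole to 2015, the lists would admit nobody, because no 2015 patient could agree to take part or wear the watch. Some split by phase is therefore needed, and the plan does not give one. The only place where screening is described is at the offer of participation, which is prospective.

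**Inputs.** From the plan: 150 per phase and a chi-square test. Assumed, because the documents give none: two-sided 5% level; one yes/no result per patient; no true effect; 15% positive if alert and 60% if disoriented; a share f = 10 / 20 / 30% of 2015 patients disoriented; a share k of disoriented patients still eligible prospectively.

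**Formulas.**
- 2015 positive rate = (1 − f) × 0.15 + f × 0.60, giving 19.5 / 24.0 / 28.5%.
- Prospective disoriented share q = fk / (1 − f + fk).
- Prospective positive rate = (1 − q) × 0.15 + q × 0.60.
- Rejection probability = sum of binomial(150) × binomial(150) probabilities over all tables with Pearson chi-square above 3.841.

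Example, f = 0.2 and k = 0.5: q = 0.10 / 0.90 = 0.111; prospective rate = 0.15 + 0.111 × 0.45 = 20.0%, against 24.0% in 2015.

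| Disoriented patients still eligible (k) | Prospective rate, f = 10 / 20 / 30% | Rejection with no true effect |
|---|---|---|
| All | 19.5 / 24.0 / 28.5% | 5 / 5 / 5% |
| Three quarters | 18.5 / 22.1 / 25.9% | 6 / 7 / 8% |
| Half | 17.4 / 20.0 / 22.9% | 8 / 13 / 20% |
| A quarter | 16.2 / 17.6 / 19.4% | 12 / 27 / 46% |
| None | 15 / 15 / 15% | 18 / 51 / 82% |

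**Sensitivity.** With f 10–30%, 5–25% positive if alert and 40–80% if disoriented, rejection runs 5–14% (three quarters eligible), 5–48% (half) and 6–100% (none).

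**Other endpoints, also on assumed rates.** Falls (Fisher's test; 3% in alert against 6–12% in disoriented patients, or 5% against 10%): 2–4% with half eligible, 2–13% with none. Length of stay (simulated rank-sum test; 20% disoriented, staying 1.25 / 1.5 / 2 times as long): 5 / 7 / 9% with half eligible, 8 / 16 / 30% with none.

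**After the fix.** If the same criterion is applied perfectly to 2015, rejection returns to about 5%. If the 2015 filter misses a share m = 0.3 of disoriented patients and none are eligible prospectively, the disoriented share left in 2015 is fm / (1 − f + fm) = 3.2 / 7.0 / 11.4%. The 2015 rate is then 16.5 / 18.1 / 20.1% against 15%, and rejection is about 6 / 11 / 21.5%.

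**Adjustment alone.** In a logistic simulation with three covariates related to disorientation (odds ratios 2, 1.5 and 1.5 per SD) and no filter on 2015, rejection falls only from 18 / 49 / 82% to 17 / 45 / 76% with none eligible.

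**The case against.** The lists stand ahead of both phase sections and carry no label, so they can be read as study-wide. The retrospective section nearly repeats the first inclusion item and may be shorthand. This stands in part: a reader might infer that the plan exempts 2015 patients from the alertness rule, but no sentence says so. One-sided screening is the more natural reading, not the only one. The gap remains on either reading, because the lists cannot be applied to 2015 whole and nothing says which parts apply.

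A reader might also take 18 / 51 / 82% as the size of the problem. Those figures require that no disoriented patient is eligible prospectively, which is the reading furthest from an exclusion that joins disorientation and inability to follow commands. The documents do not give the eligible share, and every rate is assumed, so the figures show what is possible and not what will happen.

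Finally, the study is described as observational and quasi-experimental and already discloses a convenience sample. That is fair, but neither statement tells a reader that the phases may be selected differently on a trait close to two endpoints. Selection by consent and watch-wearing, and change since 2015, will remain whatever is done. This limits what the fix can achieve but does not remove the reason for it.

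**Conclusion.** The concern holds in conditional form and should be fixed. The plan does not say which criteria govern the 2015 cohort. Followed as it most naturally reads, it compares an alertness-screened group with an unscreened one on confusion and delirium, without adjustment. The bias favours the prospective phase.

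Its size rests on the unstated share of disoriented patients, their positivity rates and the eligibility reading. It could be negligible if most disoriented patients remain eligible, moderate if half do, and large if none do. The effect on falls and stay is smaller.

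Two stronger conclusions are not supported: that the primary endpoint is compromised, and that matching the criteria would make a phase difference attributable to the programme or the watch.

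**What to change.** 1. In Inclusion Criteria and Exclusion Criteria, label each item by phase and reconcile the alertness and disorientation wording. In Retrospective Study Period, apply to 2015 every criterion readable from the record: age, alertness or orientation as reconciled and assessed at a comparable time point, C. difficile and C. auris status, recorded material allergy, and the same units. Take all eligible 2015 records, or a random 150, instead of a convenience 150.
2. Name the source of each secondary endpoint. Test between phases only those obtained from the same source in both, and report items available only from WatchRx records or prospective chart review descriptively.
3. Optionally, add a supportive analysis adjusted for age, sex, primary diagnosis and comorbidities, all listed under Measurements, without a length-of-stay offset. Stay is itself an endpoint, and same-day ambulatory-surgery stays may be recorded as zero. This does not replace step 1, because none of these covariates measures orientation.
4. In Limitations, add selection by consent and watch-wearing, calendar-time change since 2015, and imperfect recording of orientation in 2015.

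Cost: protocol and SAP wording plus a filter on a report already planned, with some record review if orientation is not a discrete field. The pool shrinks. If 2014 volume held, 433 / 2 ≈ 216 patients per half-year; removing 10 / 20 / 30% leaves about 195 / 173 / 152 before other criteria. If fewer than 150 remain, widen the 2015 window or accept a smaller group.

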## **Prospective Study Period**

Data collection starting after completion of the Parkinson's Disease Inpatient Clinical Knowledge and Management Program for staff nurses, advanced practice nurses (APN), nursing assistants, patient care technicians, case managers, adult inpatient physician assistants, pharmacists, occupational therapists, physical therapists, nurse educators, and dietitians.

- Data will be extracted from EPIC and WatchRx records from the Watch Rx Web Interface.

Data collected from the automatic dispensing cabinet barcoding database will verify accuracy and timeliness of medication.

- Unstructured data will be collected by the principle investigator (PI), designees inclusive of study staff through focused chart review on 150 patients.
- Data will be analyzed for objectives and endpoints.

This data will compare prevalence of medication errors, complications associated with administration of contraindicated medications and timing of medications, falls and falls with

injury, positive CAM and Mini-Cog Scores, length of stay and cost per case in the study population. This phase will also assess the knowledge of the clinicians regarding the basic aspects of Parkinson's Disease inpatient management, the Parkinson's Disease Inpatient Clinical Knowledge and management program and integration of the smartwatch into the PD medication management.

- Parkinson's Disease Knowledge Assessment Survey (Appendix A)
- Parkinson's Disease Inpatient Clinical Knowledge and Management Program (Appendix B)

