While the goal during hospitalization is to provide, safe and effective high quality care. 74% of PD patients receive incorrect medications (Martinez-Ramirez et al, 2015 and are at increased risk for developing complications related to medication administration. According to the Institute for Safe Medication Practices [ISMP] (2015 p. 19) “patients with PD require strict adherence to an individualized timed medication regimen of anti-parkinsonian agents.” Medications must be administered on time, based on the patient’s unique schedule. A comprehensive search of the literature from 2009 – 2015 found few studies evaluating the impact of focused integrated inter and multidisciplinary approach to managing PD patients during hospitalization. In another survey, PD patients’ perceptions is that hospital staff lacked understanding of PD, the importance of medication timeliness, and appreciation of valuable insights from patients, families and caregivers (Oguh & Videnovic, 2012).

A paradox of the U. S. healthcare system is that it leads the world in medical science and technology, yet there is limited application of technology to enhance patient-centered care in the hospital setting. In accordance with the Institute of Medicine’s (2001) quality performance goals, safety, effectiveness, timeliness, patient-centeredness, efficacy and equity, this study will integrate WatchRx system, a medication reminder system. The WatchRx system includes a

smartwatch, caregiver app and online web interface which allows clinicians to customize the medication administration time and alerts the patient and the nurse when the medication to be administered.

This study will conduct research on establishing multidisciplinary clinical guidelines in management of PD across the acute care setting. We will further explore the impact of PD medication management on patients hospital length of stay and complications associated with mismanagement. We intend to create a PD registry for Hackensack University Medical Center, and possibly expand across the Hackensack Meridian Health Network in the future. According to the New Jersey Assembly Bill 2955, December 2014, patients and/or their designated caregiver must receive discharge instructions prior to discharge from the hospital and appropriate referrals for follow-up care. This study aligns New Jersey Bill 2955 (2014) mandating the education and preparation of designated caregiver in the discharge plan of care of hospitalized PD patients.

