## **Secondary Endpoints**

- Difference in scheduled versus actual PD medication administration time
- Number of medication errors

- Number of contraindicated medications administered
- Number of falls
- Number of positive confusion scores
- Number of positive delirium scores
- Length of Stay

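### Chart review and WatchRx records are added for the prospective phase only, and the between-phase comparison is not limited to the sources that both phases share

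*Combined protocol and SAP*

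**What the plan says.** The Retrospective Study Period section takes the January–June 2015 data from EPIC: "Business intelligence will run the data and create reports with the specific data points mentioned above". It adds a second source: "Data collected from the automatic dispensing cabinet barcoding database will verify accuracy and timeliness of medication". No chart review is described for this phase.

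The Prospective Study Period section repeats the barcode sentence and widens the rest. On electronic records it says: "Data will be extracted from EPIC and WatchRx records from the Watch Rx Web Interface". It then adds: "Unstructured data will be collected by the principle investigator (PI), designees inclusive of study staff through focused chart review on 150 patients". The next bullet reads "Data will be analyzed for objectives and endpoints", and the paragraph after it begins "This data will compare prevalence of medication errors" and goes on to complications, falls, positive CAM and Mini-Cog scores, length of stay and cost.

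The Secondary Endpoints section lists the outcomes as counts, for example "Number of contraindicated medications administered", and gives no source for any of them. The Data Analysis section compares independent groups with t or Wilcoxon tests and with Fisher or chi-square tests, and mentions no adjustment.

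**The concern.** A before-and-after comparison of event counts needs events to be found in the same way in both periods. Here the prospective charts are to be read by study staff and the 2015 charts, as far as the plan says, are not. An event recorded only in narrative notes could be counted after the programme and missed before it.

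Ho2 and Ho3 rest on these secondary counts. If the extra events enter the comparison, the prospective count rises for a reason unrelated to the programme or the watch, and a true reduction looks smaller or disappears. The planned two-group tests do not correct for this. The plan also does not require the source of each event to be recorded, so the comparison could not later be restricted to shared sources without going back to the charts.

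**Working it through.** **1. Sources side by side**

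| Source | Retrospective (2015) | Prospective |
|---|---|---|
| EPIC | yes, through reports | yes |
| Barcode database | yes | yes |
| WatchRx records | no | yes |
| Focused chart review | not described | yes, 150 patients |

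Two sources are shared and two are prospective only. No section assigns an endpoint to a source or excludes events found only by the last two.

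**2. Which endpoints are exposed**

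- Falls: exposed if chart-review events are counted. Measurements lists falls without a source.
- Positive CAM and Mini-Cog: the Definitions table calls both standardized examinations, so they are exposed only if positives are also taken from notes, or if the frequency of screening differs between phases.
- Medication errors and contraindicated medications administered: exposed to a lesser extent. The barcode database verifies medication accuracy in both phases, and Measurements lists the Medication Administration Record. However, an error is not defined, and neither count is restricted to those records.
- WatchRx is a reminder system that "alerts the patient and the nurse when the medication to be administered", so it could add medication events only.
- Length of stay, barcode-verified timing and the knowledge score: little or not affected.

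**3. Size, by illustration**

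The documents give no event rates or detection rates, so there is no figure of the plan's own to reproduce and every input here is assumed. Suppose the shared sources capture the same fraction of events in both phases. Let R be the true event ratio (prospective to 2015), and s the share of counted prospective events found only by the extra sources. Then:

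apparent event ratio = R / (1 − s)

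| s | R = 0.70 | R = 1.00 (no effect) |
|---|---|---|
| 0 | 0.70 | 1.00 |
| 10% | 0.70/0.90 = 0.78 | 1/0.90 = 1.11 |
| 20% | 0.70/0.80 = 0.88 | 1/0.80 = 1.25 |
| 30% | 0.70/0.70 = 1.00 | 1/0.70 = 1.43 |

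A reduction is fully masked when s equals the relative reduction, so the 1.00 at s = 30% follows from the formula and is not evidence that s is that large.

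**4. Patients with at least one event**

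For Poisson counts with a captured 2015 mean of L events per patient:

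apparent patient ratio = [1 − exp(−0.70 L/(1 − s))] / [1 − exp(−L)]

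| s | L = 0.2231 | L = 1.0 |
|---|---|---|
| 0 | 0.72 | 0.80 |
| 10% | 0.80 | 0.86 |
| 20% | 0.89 | 0.92 |

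(L = 0.2231 means 20% of 2015 patients have an event, and L = 1.0 means 63%.) The shift is smaller than for event counts but in the same direction.

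**The case against.** The strongest reply is that the plan already has a common source. EPIC is named for both phases, the barcode sentence is identical in both, and the 2015 reports cover data points listed earlier, which plausibly means the secondary endpoints. A reader might infer from the missing endpoint-by-endpoint mapping that the counts have no source common to both phases; the documents do not support that. Nor does the Data Management line linking EPIC Hyperspace to the medical record number limit EPIC to that use. It is an incomplete list, and the two study-period sections say data are extracted from EPIC.

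Second, the Definitions table treats unstructured data as mainly text and defines discrete data separately. The counts may be meant to come from discrete fields, with chart review adding narrative only. That is a fair reading, supported by the single case report form and database. It makes leakage into the counts possible rather than certain. But the same definition allows numbers and facts within text, and the lines after the chart-review bullet do not keep its data out of the comparison.

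Third, other biases may run the opposite way. Inclusion and Exclusion Criteria require patients who are alert, consenting and not disoriented, whereas the retrospective section names only adult admissions with a Parkinson's diagnosis. If those criteria are not applied to 2015, the prospective group could show less confusion and delirium and fewer falls for that reason alone. This stands. It is a separate bias and does not remove this one, but it leaves the net direction open.

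Finally, fields that appear to be missing from the Appendix F data collection tool prove nothing, because that table is broken in the available text.

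**Conclusion.** The point holds in a limited form. EPIC and the barcode database are shared, but the prospective phase has two further sources, and nothing restricts the comparison to the shared ones. Prospective counts of falls, and of positive CAM and Mini-Cog results if taken from notes, could be raised by detection. Medication errors and contraindicated medications administered could be raised to a lesser extent.

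The size cannot be derived from the documents. The illustrated ratios of 0.78 and 0.88 in place of 0.70 rest on assumed shares of 10% and 20% and on equal capture by the shared sources in both phases. A reader might infer that the comparison will understate the benefit. The documents support only that it could, since leakage is one reading of the text and the eligibility criteria may push the other way. The primary endpoint is not in question. This should be corrected for the secondary comparisons.

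**What to change.** State in Retrospective Study Period, Prospective Study Period and Data Analysis:

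> Each between-phase secondary endpoint is derived by one identical definition and query from sources available in both phases (EPIC and the barcode database). The source of every event is recorded. Events found only by chart review or WatchRx are reported descriptively, outside the comparison.

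Also report, for each phase, the proportion of patients with a CAM and with a Mini-Cog recorded, because a common query does not equalise how often patients were screened. Check that the January–June 2015 fields can be queried. Where they cannot, report that between-phase comparison as descriptive only.

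An optional alternative is to apply the same chart-review form to the 150 retrospective charts, and only then count chart-review events in the comparison.

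The cost is wording in three sections, one source column in the Excel database and one check of the 2015 fields, with no added patients or visits. Events found only by the extra sources leave the comparison, and an endpoint without usable 2015 data loses its formal test under Ho2 and Ho3. The optional review costs staff time.

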RESEARCH QUESTION	Does Parkinson's Disease Inpatient Clinical Knowledge and Management Program and the WatchRx System make a difference in the clinician knowledge, customized PD order time and PD medication administration time, complications (administered contraindicated medication, falls, positive delirium scores, and positive confusion), medication error and length of stay during hospitalization?
HYPOTHESIS	
Ho1:
 
Parkinson's Disease Inpatient Clinical Knowledge and Management Program will not make a difference in the clinician knowledge.
 
Ha1:
 
Parkinson's Disease Inpatient Clinical Knowledge and Management Program will make a difference in the clinician knowledge.
 
Ho2:
 
Parkinson's Disease Inpatient Clinical Knowledge and Management Program will not make a difference in the customized PD order time and PD medication administration time, complications (administered contraindicated medication, falls, positive delirium scores, and positive confusion), medication error and length of stay during hospitalization.
 
Ha2:
 
Parkinson's Disease Inpatient Clinical Knowledge and Management Program will make a difference in the customized PD order time and

Protocol Synopsis	
	
PD medication administration time, complications (administered contraindicated medication, falls, positive delirium scores, and positive confusion), medication error and length of stay during hospitalization.
 
Ho3:
 
WatchRx System will not make a difference in the customized PD order time and PD medication administration time, complications (administered contraindicated medication, falls, positive delirium scores, and positive confusion), medication error and length of stay during hospitalization.
 
Ha3:
 
WatchRx System will make a difference in the customized PD order time and PD medication administration time, complications (administered contraindicated medication, falls, positive delirium scores, and positive confusion), medication error and length of stay during hospitalization.

STUDY DESIGN	
Two Part Study Design
 
 
• Part 1: Retrospective Phase
 
• Part 2: Prospective Phase
 

INTERVENTION	Clinician Education Program, WatchRx system, and enrollment in PD registry.
SAMPLE SIZE	
Patients - 300 in total
 
150 - retrospective phase
 
150 - prospective phase

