### STUDY SPONSOR

Hackensack University Medical Center  
[name]  
[name]

---

Definitions	
Discrete data	Data with numerical value that is distinct and separate
MDR	The Multidisciplinary (MDR) is the clinical infrastructure supporting a multidisciplinary/interdisciplinary framework for clinical practice promoting a patient-centered, evidence- and value-based care within a managed care environment
Dementia Assessment Method	Standardized examination used to detect dementia (Mini-Cog)
Delirium Assessment	Standardized examination used to detect delirium (CAM).
Unstructured data	Unstructured Data (or unstructured information) refers to information that either does not have a pre-defined data model or is not organized in a pre-defined manner. Unstructured information is typically text-heavy, but may contain data such as dates, numbers, and facts.

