## **Hypothesis**

Ho1:

Parkinson's Disease Inpatient Clinical Knowledge and Management Program will not make a difference in the clinician knowledge.

Ha1:

Parkinson's Disease Inpatient Clinical Knowledge and Management Program will make a difference in the clinician knowledge.

Parkinson's Disease Inpatient Clinical Knowledge and Management Program will not make a difference in the customized PD order time and PD medication administration time, complications (administered contraindicated medication, falls, positive delirium scores, and positive confusion), medication error and length of stay during hospitalization.

Ha2:

Parkinson's Disease Inpatient Clinical Knowledge and Management Program will make a difference in the customized PD order time and PD medication administration time, complications (administered contraindicated medication, falls, positive delirium scores, and positive confusion), medication error and length of stay during hospitalization.

Ho3:

WatchRx System will not make a difference in the customized PD order time and PD medication administration time, complications (administered contraindicated medication, falls, positive delirium scores, and positive confusion), medication error and length of stay during hospitalization.

Ha3:

WatchRx System will make a difference in the customized PD order time and PD medication administration time, complications (administered contraindicated medication, falls, positive

delirium scores, and positive confusion), medication error and length of stay during hospitalization.

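### The delirium and confusion endpoints count every positive score as a complication of the stay, with no rule separating new positives from impairment present at admission

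*Combined protocol and SAP*

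**What the plan says.** The hypotheses group "falls, positive delirium scores, and positive confusion), medication error and length of stay during hospitalization" as outcomes that the Program and the WatchRx System may change. The corresponding items under Secondary Endpoints, repeated in the Protocol Synopsis, are "Number of positive delirium scores" and "Number of positive confusion scores".

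The Prospective Study Period section states the comparison. It opens with "This data will compare prevalence of medication errors" and its list goes on to "injury, positive CAM and Mini-Cog Scores, length of stay and cost per case in the study population".

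The Definitions table gives each instrument one purpose. For CAM it is "Standardized examination used to detect delirium (CAM"; for Mini-Cog it is "Standardized examination used to detect dementia (Mini-Cog". No instrument is assigned to confusion.

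The Inclusion Criteria ask for alert patients who can follow commands, and the Exclusion Criteria remove those who are disoriented and cannot. The Retrospective Study Period section defines the 2015 cohort by diagnosis and admission dates only. Measurements lists neither CAM nor Mini-Cog, and Data Analysis offers only unadjusted group comparisons.

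**The concern.** A complication of a hospital stay should begin during the stay. As written, a patient who arrives with delirium, or with a dementia that Mini-Cog detects, can score positive whatever the Program or the watch does, and that positive enters the comparison like any other.

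Two consequences follow.

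- **Dilution.** Positives that neither intervention could prevent sit in both phases and pull the ratio towards 1.
- **Possible bias.** If the alertness and orientation criteria screen the prospective patients but not the 2015 patients, the phases start with different shares of impaired patients. The difference would then look like a benefit.

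What is at stake is the delirium and confusion part of both secondary objectives. The primary endpoint, clinician knowledge, is not affected.

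**Working it through.** **1. The text.** Four statements have to be read together: these scores are complications during hospitalization (Hypothesis); the endpoint is the number of positives (Secondary Endpoints); prevalence is what is compared (Prospective Study Period); and Mini-Cog detects dementia (Definitions). No section adds a restriction to new positives, requires a score at admission, or adjusts for status at admission.

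**2. The plan's own figure.** Sample Size Calculation gives 150 + 150 = 300 patients as a convenience sample. It states no alpha, power, event rate or effect size, so there is no power figure to reproduce.

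**3. Dilution (illustration).** From the plan: n = 150 per phase. Assumed, because the documents give no rates: two-sided alpha 5%; new-onset risk among admission-negative patients of 20% in the retrospective and 10% in the prospective phase; the same share π positive at admission in both phases. The outcome is simplified to yes/no per patient.

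- Observed proportion: p = π + (1 − π) × new-onset risk
- Share of retrospective positives already present at admission: π / p1
- Power: Φ[(d − 1.96 × se0) / se1], where d = p1 − p2, se0 = √(2 p̄(1 − p̄)/n), se1 = √(p1(1 − p1)/n + p2(1 − p2)/n), and p̄ is the mean of p1 and p2

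For π = 20%:

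- p1 = 0.20 + 0.80 × 0.20 = 0.36 and p2 = 0.20 + 0.80 × 0.10 = 0.28, so the ratio is 0.28/0.36 = 0.78.
- se0 = 0.0539 and se1 = 0.0537, so power = Φ[(0.08 − 1.96 × 0.0539)/0.0537] = 0.32.
- New positives only: n = 150 × 0.80 = 120, 0.20 against 0.10, se0 = 0.0461, se1 = 0.0456, power 0.58.

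| π | Observed, retrospective vs prospective | Ratio | Share already present, retrospective | Power, all positives (n = 150) | Power, new positives only (n per phase) |
|---|---|---|---|---|---|
| 10% | 28% vs 19% | 0.68 | 36% | 45% | 63% (135) |
| 20% | 36% vs 28% | 0.78 | 56% | 32% | 58% (120) |
| 30% | 44% vs 37% | 0.84 | 68% | 23% | 53% (105) |
| 40% | 52% vs 46% | 0.88 | 77% | 18% | 47% (90) |

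The new-onset ratio is 0.50 in every row.

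**4. Unequal admission status (illustration).** Assume no effect at all: 15% new positives in both phases. If 30% of retrospective and 20% of prospective patients are positive at admission, the observed proportions are 0.30 + 0.70 × 0.15 = 40.5% and 0.20 + 0.80 × 0.15 = 32.0%. With the same approximation, counting both tails, the test rejects about 33% of the time instead of 5%. For 30% against 25% it rejects about 12%; for 40% against 20%, about 85%.

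**The case against.** **Eligibility already deals with this.** In part. The alertness and orientation criteria, together with informed consent, should keep some overtly delirious patients out of the prospective phase. They use neither CAM nor Mini-Cog, and an alert patient with dementia who follows commands still qualifies. Nor are they restated for the 2015 cohort, which is where the possible imbalance comes from.

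**Mini-Cog is not named as the confusion score.** Correct. A reader might infer the link because CAM and Mini-Cog are the only cognitive instruments named and CAM belongs to delirium, but it remains an inference. Mini-Cog also appears in a list that includes cost per case, so its presence there does not make it a complication. What the text does support is that Mini-Cog positives are compared between phases as an outcome and that the confusion endpoint has no stated instrument.

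**The plan openly says prevalence.** It does, but prevalence on its own does not answer a question about complications during the stay.

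**The illustration is not the stated endpoint.** This stands. The endpoint counts scores, while the calculation uses one yes/no outcome per patient. Repeat screening of the same impaired patient could add positives, but the documents give no screening schedule, so that effect cannot be sized.

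**The impact is limited.** These are two of seven secondary endpoints, and under the assumed rates power stays at 63% or below even after the change. The reason to change is that the endpoint should match its objective; the gain in power is secondary.

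**Conclusion.** The concern holds as a defect in endpoint definition; no stated number is wrong. Following the plan as written mixes status on arrival into an outcome described as a complication of the stay. For CAM the issue is acute delirium already present at admission; for Mini-Cog it is dementia.

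Under the assumed rates, a true halving of new positives would appear as a ratio of 0.68 to 0.88, and power would be 45% to 18% instead of 63% to 47%. These figures rest on assumed admission positivity of 10% to 40%, assumed new-onset risks, and a per-patient outcome.

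Two stronger readings are tempting and are not supported.

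- A reader might infer that these endpoints mostly measure impairment on arrival. The documents give no prevalence, and at 10% positive on admission only 36% of retrospective positives would be pre-existing.
- A reader might infer that the comparison is certainly biased towards the Program. That follows only if the eligibility screen acts on the prospective phase alone, which the documents leave open.

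**What to change.** 1. **Delirium.** In the Protocol Synopsis and Secondary Endpoints, define the endpoint as at least one positive CAM after a negative first CAM of the admission, applied alike in both phases. Report raw counts of positive scores as descriptive only.
2. **Mini-Cog.** Do not use it as an outcome. Report the first Mini-Cog of the admission as a baseline characteristic and, where available, adjust for it in a logistic model of new-onset positive CAM. That model has to be added to Data Analysis.
3. **Confusion.** Either name the instrument and count only positives after a negative admission score, or drop the endpoint and amend the matching research question, hypotheses and objectives.
4. **Eligibility.** Apply the alertness and orientation criteria to the 2015 cohort as far as the charts allow.
5. **Data.** Add dated CAM and Mini-Cog results to Measurements.

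The main cost is wording, dated scores and one added model. Patients who are positive or unscreened at admission leave the denominator, so report their number by phase. No section says that an admission CAM was recorded in 2015. If those scores are sparse, dropping unscreened patients could select the two phases differently, and this should be stated as a limitation.
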